[figure not shown]

Association between Vitamin D and The Development of Uterine Fibroids

2018.3.15

Study objectives The primary objective of this part is to assess the efficacy of supplementation with vitamin D on inhibiting the development of uterine fibroids in one year and two years. The secondary objective of this study is to evaluate the safety of supplementation with vitamin D in subjects.

Trial design This is an open-label, randomised controlled trial. After signing of informed consent, patients with vitamin D deficiency ($12 \text{ ng/ml} \leq \text{Serum 25-hydroxyvitamin D}_3 < 20 \text{ ng/ml}$) and uterine fibroids will be randomly assigned in a 1:1 ratio to intervention group A or control group B. Intervention group A will accept an oral dose of 1600 IU/day vitamin D₃ for up to 2 years. Control group B will receive 2 years follow-up. Patients with vitamin D insufficiency ($20 \text{ ng/ml} \leq \text{Serum 25-hydroxyvitamin D}_3 < 30 \text{ ng/ml}$) and uterine fibroids will be randomly assigned in a 1:1 ratio to intervention group C or control group D. Intervention group C will accept an oral dose of 800 IU/day vitamin D₃ for up to 2 years. Control group D will receive 2 years follow-up. Gynecologic ultrasound examinations will be performed every three months. The mount, location and size of the uterine fibroids will be documented (the transverse, longitudinal, and antero-posterior diameters of fibroids will be documented at each efficacy ultrasound examination for volume calculation). Percent change in volume of the total fibroids compared to baseline in different groups (baseline = last value obtained before randomization). Three perpendicular diameters (d₁, d₂, and d₃) were collected for each fibroid, and the volume of each fibroid (in cm³) was calculated with the ellipsoid formula: $4/3 * \pi * (d_1 * d_2 * d_3)/8$. For each patient, the total volume of fibroids (defined as the sum of the volumes of all the fibroids detected) was also calculated. The safety of vitamin D in subjects with uterine fibroids will be evaluated, including blood routine examination, electrolyte, hepatic and renal function, liver and urinary system ultrasound, and serum 25-hydroxyvitamin D₃. Vitamin D₃ Drops are purchased from Sinopharm star shark pharmaceutical (xiamen) co., LTD. An overview of the study design is shown in Figure 2 and Table 2.

[figure not shown]

Figure 2 flow diagram.

Table 2:time of date collection

Follow-up	1	2	3	4	5	6	7	8	9

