Months	0	3	6	9	12	15	18	21	24
The form of follow-up	Out-patient								
Informed consent	X								
Medical history	X								
Physical examination	X								
Serum 25-hydroxyvitamin D ₃	X	X	X	X	X	X	X	X	X
Urine pregnancy test	X	X	X	X	X	X	X	X	X
Gynecologic ultrasound	X	X	X	X	X	X	X	X	X
Hepatic and renal function	X		X		X		X		X
Electrolyte	X		X		X		X		X
Blood routine examination	X		X		X		X		X
Liver and urinary		X			X				X
System ultrasound			X						
Side-effect assessment		X	X	X	X	X	X	X	X
Changes in menstruation		X	X	X	X	X	X	X	X
Adverse event assessment		X	X	X	X	X	X	X	X
Vitamin D receptor genotype	X								

Sample size According to a previous study, the volume of uterine fibroids was 8.2 (2.1-30.5) cm³ after the supplement of vitamin D 12 months and 11.4 (5.5-22.3) cm³ in the control group, respectively. On the basis of a 0.9 power to detect a significant difference ($\alpha=0.05$, one-sided), 320 participants will be required for the four groups and in a 1:1:1:1 ratio. Allowing for a 10% withdrawal rate, we plan to include 360 patients in the whole trial.

Inclusion criteria

1. Patients are willing to cooperate with the follow-up and sign informed consent;
2. Females aged 35-50 who are diagnosed as having uterine fibroids by transvaginal or abdominal ultrasonography;
3. The maximum average diameter of intramural myoma is $\leq 4\text{cm}$, $\geq 1\text{cm}$; The amount of myoma is less than 4;
4. Serum 25-hydroxyvitamin D₃ $< 30\text{ ng/ml}$, $\geq 12\text{ ng/ml}$.

Exclusion criteria

1. Patients with heavy menstrual bleeding ($>80.0\text{ mL}$), menstrual disorders, pelvic discomfort, infertility, or other indications for operation;

2. Patients complicated with myoma degeneration and adenomyosis that were suspected or diagnosed by ultrasound or gynecologic examination;
3. Allergic to vitamin D₃;
4. Use of sexual hormone, mifepristone, gonadotropin-releasing hormone agonist (GnRHa), or other medication which is likely to interfere with uterine fibroids within 3 months;
5. Pregnancy, lactation, postmenopause, or planned pregnancy within two years;
6. Suspected or identified as other tumors of genital tract;
7. History of osteoporosis or vitamin D deficiency taking vitamin D supplements within previous one month;
8. History of autoimmune diseases, infectious diseases (tuberculosis, AIDS), autoimmune diseases, digestive system diseases (malabsorption, crohn disease, and dysentery);

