9. Alanine aminotransferase (ALT) or aspartate transaminase (AST) more than 3 times of the normal upper limit, total bilirubin (TBIL) more than 2 times of the normal upper limit;
10. Creatinine levels ≥ 1.4 mg/dL (123 μ mol/L) or creatinine clearance ≤ 50 mL/min;
11. History of malignant tumors;
12. Simultaneous participation in another clinical study with investigational medicinal product(s) or researcher thinks the subjects are not suitable for this trial.

Outcomes measures Primary outcomes: percent change in volume of the largest fibroid and total fibroids compared to baseline (baseline = last value obtained before randomization; measured by ultrasound examination). Secondary outcomes: percentage of subjects undergoing other medical or surgical treatment, hypercalcemia, urinary calculus, abnormal liver and renal function. Ultrasound examinations will be performed by a physician well experienced in gynecology. If possible, the same examiner should conduct all examinations of a subject throughout the study and the same ultrasound machine (per site) should be used throughout the study. For each subject, the most appropriate ultrasound method (transvaginal or abdominal) should be used depending on fibroids location and this method should be used consistently throughout the study.

Withdrawal Subjects must be withdrawn from the study when one of the following criteria occurs:

1. At their own request. At any time during the study and without giving reasons, a subject may decline to participate further. The subject will not suffer any disadvantages as a result;
2. In the investigator's opinion, continuation of the study treatment would be harmful to the subject's health;
3. Obvious non-compliance;
4. Lost to follow-up;
5. Pregnancy;
6. Other medical or surgical treatments of uterine fibroids.
7. Receive other medical treatments which may affect the level of serum 25-hydroxyvitamin D₃ or other surgical treatments.

8. The level of serum calcium > 3.5 mmol/L or serum 25-hydroxyvitamin D₃ > 100 ng/mL.

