Safety assessments Safety will be assessed by renal and liver function test, electrolyte, routine blood test, and serum 25-hydroxyvitamin D₃. Urine pregnancy test and serum 25-hydroxyvitamin D₃ level will be detected every three months. Other indicators are detected during the period of screening and after the treatment of every six months. Liver and urinary system ultrasound will be conducted after the treatment of 12 months and 24 months. The occurrence of any adverse events in trial participants will be recorded in the case report forms during each patient visit. We will withdraw patients who have severe adverse events, as it is unsafe for them to continue the trial. Meanwhile, we will give them relevant medical care and follow them up until the reaction has terminated.

Statistical analysis Statistical analyses will be performed using SPSS version 22.0 for Windows (SPSS Inc., Chicago, IL, USA). The randomisation sequence is generated by the use of the SPSS software. The normality of distribution of continuous variables are tested by one-sample Kolmogorov-Smirnov test. Continuous variables with normal distribution are reported as mean (standard deviation); non-normal variables are presented as median (interquartile range). Means of 2 and 3 or more continuous normally distributed variables, respectively, are compared by independent samples Student's t test or one-way ANOVA test. Mann-Whitney U test and Kruskal-Wallis test are used, respectively, to compare means of 2 and 3 or more groups of variables not normally distributed. The frequencies of categorical variables are compared using Pearson χ^2 or Fisher's exact test, when appropriate. A value of $P < 0.05$ is considered significant.

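### Statistical analysis lists only unadjusted tests although baseline fibroid volume is measured on every woman; adjusting for it would give a modest, nearly free gain in precision

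*Combined protocol and SAP*

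**What the plan says.** Outcomes measures defines the primary outcomes as "percent change in volume of the largest fibroid and total fibroids compared to baseline", with "baseline = last value obtained before randomization". The objective refers to "inhibiting the development of uterine fibroids in one year and two years".

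For continuous variables, Statistical analysis offers two routes. For normally distributed ones, "Means of 2 and 3 or more continuous normally distributed variables, respectively, are compared by independent samples" t tests, or by one-way ANOVA. For the rest, "Mann-Whitney U test and Kruskal-Wallis test are used, respectively, to compare means of 2 and 3 or more groups of variables not normally distributed". Categorical variables get chi-square or Fisher tests. The section contains no ANCOVA, regression, mixed model or other analysis that takes a covariate. It does not say which listed test applies to the primary outcomes.

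The baseline data exist. Trial design states that "the transverse, longitudinal, and antero-posterior diameters of fibroids will be documented at each efficacy ultrasound examination for volume calculation", and Table 2 schedules gynecologic ultrasound and serum 25-hydroxyvitamin D at month 0. Age is known through eligibility ("Females aged 35-50 who are diagnosed as having uterine fibroids"). Baseline information enters the plan in two ways only: as the denominator of percent change, and through separate randomisation within two 25-hydroxyvitamin D bands (A v B and C v D).

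**The concern.** Dividing by baseline is not the same as adjusting for it. On the log scale, percent change forces the slope of follow-up on baseline to be 1. With equal variances at the two times the actual slope is rho, and for any rho below 1 the change stays negatively related to baseline: women with large fibroids at entry tend to show smaller relative growth, and the reverse. An unadjusted test puts that dependence into the error term. If the two arms happen to differ at baseline, it also goes into the estimated treatment difference.

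Baseline volume varies widely. By the plan's ellipsoid formula, an intramural fibroid of 1 cm is 4/3 × π × 1/8 = 0.52 cm³ and one of 4 cm is 4/3 × π × 64/8 = 33.5 cm³, and a woman may have up to three fibroids. No stratification by fibroid volume is described, so only the analysis can deal with an imbalance. What is at stake is efficiency, and an estimate that moves with chance baseline differences. The validity of the test is not at stake.

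**Working it through.** **Inputs from the document.** Sample size gives 320 women in a 1:1:1:1 ratio, so 80 per arm, with 90% power at one-sided 0.05. The control planning value is 11.4 (5.5-22.3) cm³.

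**Assumptions, not in the document.** Rho, the correlation of log baseline with log follow-up volume, is taken as 0.6, 0.8, 0.9 and 0.95. Log-scale variances are equal at both times.

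**The plan's own figure.** The withdrawal step is close: 320/0.9 = 356, against 360 stated. The 80 per arm does not follow from the stated medians and intervals. Read as interquartile ranges, they give 501 per arm on the raw scale (pooled SD 17.3) or 396 on the log scale (pooled SD 1.58). That is a separate matter. Here the effect that 80 per arm would detect with 90% power (one-sided 5%) serves only as a benchmark: (1.645 + 1.282) × √(2/80) = 0.463 SD of log change, a non-centrality of 2.926.

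**Step 1, variance.** With log-scale variance σ² at each time, the variance of log change is 2σ²(1 − rho) and the ANCOVA residual variance is σ²(1 − rho²). The ratio is (1 + rho)/2, and the equivalent number per arm is 80 × ratio.

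**Step 2, power at two-sided 5%, 80 per arm.** Unadjusted t test on log change: Φ(2.926 − 1.960) = 83.3%. Adjusted: Φ(2.926/√ratio − 1.960).

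| rho | Variance ratio | Equivalent n per arm | Adjusted power | Gain (points) |
|---|---|---|---|---|
| 0.6 | 0.80 | 64 | 90.5% | 7.2 |
| 0.8 | 0.90 | 72 | 87.0% | 3.7 |
| 0.9 | 0.95 | 76 | 85.1% | 1.8 |
| 0.95 | 0.975 | 78 | 84.2% | 0.9 |

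Simulation at 80 per arm agrees within its error, with gains of about 7, 3 to 4, 2 and 1 points. At rho 0.6, 0.8 and 0.9 one run gave 83/83/82% for the unadjusted t test on log change and 89/87/84% for ANCOVA. Type I error was 4-6% for every method.

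**Step 3, the fair comparator.** Mann-Whitney on percent change gave 81/82/80% in the same run. Setting ANCOVA against that mixes the efficiency loss of a rank test with the effect of adjustment. The gains in the table are for adjustment alone.

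**Step 4, chance imbalance.** Reading the control interval as an interquartile range, the log-SD is ln(22.3/5.5)/1.349 = 1.04. The SD of the arm difference in mean log baseline is 1.04 × √(2/80) = 0.164. An imbalance of 2 SD (0.33) shifts the unadjusted difference in log change by (1 − rho) × 0.33, which is 0.13, 0.07 and 0.03 log units at rho 0.6, 0.8 and 0.9. The standard error of that difference is 1.04 × √(2(1 − rho)) × √(2/80) = 0.147, 0.104 and 0.074. The shift is therefore √(2(1 − rho)) = 0.89, 0.63 and 0.45 of a standard error. A 1-SD imbalance gives half of this.

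**The case against.** The strongest reply is that nothing here is an error. Randomisation makes the unadjusted tests valid. Their standard error already includes the variation from chance imbalance, and a 2-SD imbalance is roughly a 1-in-20 event. Percent change already removes the proportional part of baseline. Outcomes measures asks for the same examiner and machine where possible and a consistent ultrasound method, which limits measurement noise and may push rho up. At log-SD 1.04, rho 0.6 implies an SD of log change of 0.93, about a 2.5-fold change, so the largest gains rest on volumes being quite unstable. All of this stands, and it limits the size of the point. It does not remove it: for every rho below 1 in this model, adjustment does better.

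A reader might infer three stronger things that the document does not support.

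- **That the planned analysis is biased or inflates false positives.** It does not; null rejection was 4-6%.
- **That age and baseline 25-hydroxyvitamin D also carry lost precision.** No gain from either is shown. The document gives nothing on how strongly age predicts growth, and randomising within bands already limits imbalance in 25-hydroxyvitamin D.
- **That the plan assigns a two-sample test to each primary outcome.** The section is a general list that also includes tests for three or more groups. Two-arm comparisons are inferred from the A v B and C v D design.

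Nor is adjustment on the log scale free of drawbacks. Total volume is the sum over fibroids detected, so it could be zero at follow-up, and its log would then be undefined.

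**Conclusion.** The point holds as a recommended improvement, not as a defect that undermines the trial. It is certain that the plan lists no baseline-adjusted analysis and that baseline volume is available. The size is uncertain because rho is not documented: over rho 0.6 to 0.95 the saving is equivalent to about 16 down to 2 women per arm of 80, or about 7 down to 1 percentage points of power at two-sided 5%. Above a rho of about 0.9 the benefit is small. These figures assume equal log-scale variances and the benchmark effect of 0.463 SD. The absolute power levels are illustrative, because the stated sample size could not be reproduced from its inputs; the variance ratios do not depend on it.

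**What to change.** In Statistical analysis, prespecify the primary comparison as an ANCOVA of log follow-up volume on arm and log baseline volume. Do this separately for A v B and C v D, at 12 and at 24 months, and for both largest-fibroid and total volume. Report the back-transformed ratio (percent difference) with a 95% confidence interval.

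State in advance what happens when no fibroid is detected: for example a small fixed floor value, or a rank ANCOVA of percent change on baseline volume, which needs no log. Age and baseline 25-hydroxyvitamin D may be added as covariates if they are named beforehand, but not on the expectation of a demonstrated gain. Keep the unadjusted percent-change comparison as a sensitivity analysis.

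The cost is some plan wording and a few lines of code; no new data, visits or patients are needed. The trade-offs are an assumption of linearity in log baseline, a summary measure that becomes a ratio of geometric means, and the need for the zero-volume rule.

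### One unsided P < 0.05 rule covers two primary outcomes, two time points and two randomised pairs, and no test is tied to a primary comparison

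*Combined protocol and SAP*

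**What the plan says.** Trial design randomises within two vitamin D strata. For deficient women, those with "uterine fibroids will be randomly assigned in a 1:1 ratio to intervention group A or control group B"; for insufficient women, those with "uterine fibroids will be randomly assigned in a 1:1 ratio to intervention group C or control group D". The one sentence that links the volume outcome to groups reads "Percent change in volume of the total fibroids compared to baseline in different groups", and it names no pair.

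Study objectives sets two horizons: "inhibiting the development of uterine fibroids in one year and two years". Outcomes measures lists two primary outcomes, percent change in the volume of the largest fibroid and of all fibroids together, and gives no time point.

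Statistical analysis assigns tests by distribution and number of groups. Normally distributed variables "are compared by independent samples Student's t test or one-way ANOVA test"; for the rest, "Mann-Whitney U test and Kruskal-Wallis test are used, respectively, to compare means of 2 and 3 or more groups". The only decision rule is "A value of $P < 0.05$ is considered significant". It has no side, no hierarchy and no multiplicity rule.

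Sample size does state a side (one-sided, 0.05). It gives 320 patients in four equal groups "On the basis of a 0.9 power to detect a significant difference", without saying between which groups.

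**The concern.** A plan should fix, before the data are seen, which result decides the trial. Here two pairs, two outcomes and two time points give 2 x 2 x 2 = 8 tests. Any of them could be presented as the primary result, and the rule does not say how many must succeed. This matters more in an open-label trial.

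Two further gaps follow. The side of the test is stated for the sample size but not carried into the analysis, and ANOVA and Kruskal-Wallis have no direction. The listed tests for three or more groups also leave a four-group efficacy test open. Such a test mixes the randomised contrasts with contrasts between deficient and insufficient women, who were not randomised to their stratum.

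**Working it through.** **1. The plan's own sample size.** Inputs from Sample size: 8.2 (2.1-30.5) vs 11.4 (5.5-22.3) cm³, one-sided 0.05, power 0.9, 320 in total (80 per group). Formula: n per group = 2 x (1.645 + 1.282)² x (SD/difference)².

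- Spread read as an interquartile range, raw scale: difference 3.2. Pooled SD 17.3 gives 501 per group (2,004 for four); control SD 12.5 gives 260 (1,040).
- Same reading, log scale: difference ln(11.4/8.2) = 0.329. Pooled SD 1.58 gives 396 (1,584); control SD 1.04 gives 170 (680 for four groups, 340 for two).
- Spread read as a 95% range (assumption), raw scale: pooled SD gives 240 for four groups; the vitamin D group's SD gives 352.

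None of these gives 320. With an interquartile range and pooled SD, power at 80 per group is 32% (raw) or 37% (log). The type of spread and the test are not stated, so this does not show which number is right. The withdrawal step does reproduce: 320/0.9 = 356, close to 360. The power figures in step 4 therefore take the stated 0.9 at face value.

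**2. False positives within one pair (four tests).** The test statistics are drawn as correlated normals with no effect. Assumed correlations are 0.7-0.95 between outcomes and 0.5-0.9 between time points, with their product for a different outcome at a different time. The chance that at least one of four is significant, from the highest correlations to the lowest, is:

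| Rule | One pair (4 tests) | Both pairs (8 tests) |
|---|---|---|
| One-sided 0.05 | 9-14% | 16-26% |
| Two-sided 0.05, either direction | 9-15% | 17-28% |
| Two-sided 0.05, favouring vitamin D | 5-7% | 9-14% |

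The nominal rates for a single test are 5%, 5% and 2.5%.

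**3. From one pair to two.** The pairs contain different patients and are independent, so the eight-test rate is 1 - (1 - p)². Before rounding, the one-sided four-test rates are 8.5% and 13.8%: 1 - 0.915² = 16% and 1 - 0.862² = 26%. With one outcome and one time point, two pairs give 1 - 0.95² = 9.75% one-sided. Two-sided, the rate in favour of vitamin D is 1 - 0.975² = 4.9%.

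**4. Side and meaning of the 0.9 (conditional).** The planned standardised difference is 1.645 + 1.282 = 2.926.

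- Two-sided 0.05: Phi(2.926 - 1.960) = 83%. Restoring 90% needs a factor of ((1.960 + 1.282)/2.926)² = 1.227, so 320 becomes 393, or 4 x 99 = 396 in equal groups (396/0.9 = 440 with 10% withdrawal).
- If 0.9 refers to 160 vs 160, one pair of 80 vs 80 has Phi(2.926/√2 - 1.645) = 66% one-sided for the same effect.
- Holm over two pairs, if 0.9 is per pair, one-sided: 0.833 + 0.067 x 0.833 = 89% per pair when both effects are as planned, and 83% when only one is. With a two-sided family these become 81% and 76%.

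**5. A four-group efficacy test.** Take no vitamin D effect, 80 per group, and strata that differ in mean outcome by d SD. ANOVA is noncentral F(3, 316) with noncentrality 80 x d². It rejects in 5%, 10%, 29% and 60% of trials for d = 0, 0.1, 0.2 and 0.3. The documents give no value for d.

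**The case against.** **The comparisons are fixed by design.** Each stratum has its own control and dose, so A vs B and C vs D are the natural reading, and ANOVA has an obvious use in describing four groups at baseline. This largely stands. A reader might infer that the plan will test efficacy across four groups, or that stratum differences will pass for a vitamin D effect. The documents support neither: they leave the test open but do not announce it, and they report no difference in growth between strata. At d = 0 the test keeps its 5%.

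**Two-sided results include harm.** A reader might take 17-28% as the chance of a false claim for vitamin D. It is not, because about half of those results point the other way. The relevant two-sided figure is 9-14% over eight tests.

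**The pairs are separate questions.** They are different populations on different doses, and adjustment across them can be argued either way. This stands. It does not remove the problem, because two outcomes at two time points within one pair already exceed the nominal rate. Under two-sided testing that excess is modest: 5-7% in favour of vitamin D against a nominal 2.5%, which is close to the 5% of a one-sided test.

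**The power is not established.** This stands too. The stated inputs do not yield 320, so neither 90% nor 83% is shown to be the trial's real power.

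**The listed tests are adequate.** A reader might infer that a log-volume model with baseline volume as a covariate is needed. The documents do not show this. In a simulation with assumed inputs (one fibroid per patient, log-growth SD 0.6, effect -0.2 on the log scale, two-sided 0.05), one pair had 50% power with Mann-Whitney and 52% with a log model. Adding the baseline covariate to log change left it at 52%.

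**Conclusion.** The point holds, and the plan should be changed. Its one stated decision rule, applied to the outcomes, time points and pairs it names, gives a false-positive chance of 16-26% one-sided, or 17-28% two-sided with 9-14% in favour of vitamin D. The excess is present within a single pair, so it does not depend on treating the pairs as one family. The sizes rest on the assumed correlations; the direction does not.

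The mismatch of side is a matter of text. Its cost, 90% to 83%, is conditional on a 0.9 that the stated inputs do not reproduce and that is not assigned to a comparison. The four-group test is a gap to close, not a demonstrated error.

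**What to change.** 1. State that efficacy is compared only within the randomised pairs (A vs B, C vs D) or by a contrast stratified on vitamin D status. Keep four-group ANOVA and Kruskal-Wallis for baseline description.
2. Name one primary outcome and time point, for example percent change in total volume at 12 months, the interval in the sample-size source. Make the others secondary, or test them in a fixed order within each pair.
3. State the position on the two pairs: Holm, a stratified combined contrast, or two separate questions each tested at 0.05 with that justification. Any of these is defensible if chosen before analysis.
4. Match the side: test one-sided at 0.05 as in Sample size, or test two-sided and restate the power. Say which comparison the 0.9 refers to.

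A log-volume model adjusted for baseline volume and stratum is optional as a sensitivity analysis.

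**Cost.** The change is to wording only; the visit schedule already has ultrasound at baseline, 12 and 24 months. Fewer results can be called primary. If 0.9 is per pair, Holm lowers per-pair power from 90% to 83-89% one-sided, or from 83% to 76-81% two-sided. The combined contrast averages two dose-stratum pairs and loses power if only one stratum responds.

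### Safety event frequencies are compared only by significance tests, with no effect estimate or confidence interval, in groups of 80 to 90 that can show little about uncommon harms

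*Combined protocol and SAP*

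**What the plan says.** The Study objectives section states: "The secondary objective of this study is to evaluate the safety of supplementation with vitamin D in subjects". Outcomes measures lists the binary safety outcomes among the secondary outcomes: "hypercalcemia, urinary calculus, abnormal liver and renal function".

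The Statistical analysis section has one sentence on such outcomes. It begins "The frequencies of categorical variables are compared using Pearson" chi-square and ends with the alternative "Fisher's exact test, when appropriate". The section closes by saying that a P value below 0.05 "is considered significant". It does not say whether tests are one- or two-sided, when Fisher replaces Pearson, or whether frequencies are compared in pairs or across all four groups. It plans no risk difference, confidence interval or acceptable excess, and does not mention combining the two supplemented groups.

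The Sample size section rests on fibroid volume alone. Its alpha is 0.05, and it reads "one-sided), 320 participants will be required for the four groups". Neither the power of 0.9 nor the quoted volumes concern safety.

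**The concern.** The named harms are likely to be uncommon, and the group sizes were set for a different outcome. A significance test on a few events in groups of this size will often be non-significant even when supplementation causes real excess harm. If the P value is the only comparative result, the reader cannot see how large an excess remains compatible with the data. The error would run towards missing harm, in a trial where two of the four groups take a daily supplement for up to two years.

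The test rule is also loose. With few events, Pearson and Fisher can fall on opposite sides of 0.05 for the same table, so the reported result could depend on a choice made after the data are seen.

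**Working it through.** **Group size.** Inputs from the Sample size section: 320 evaluable, four equal groups, 10% withdrawal, 360 enrolled.
- 320/4 = 80 evaluable per group.
- 320/(1 − 0.10) = 355.6, so 356. The plan states 360, which agrees after rounding up, and 360/4 = 90 per group.

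The calculations below therefore use 80 to 90 per group.

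**Five events against none, 90 per group.** The event counts are illustrative.
- Smallest expected count: 5 × 90/180 = 2.5. This is below 5, so Fisher is the conventional choice.
- Fisher, one-sided: C(90,5)/C(180,5) = 43,949,268/1,488,847,536 = 0.030.
- Fisher, two-sided: twice that, 0.059.
- Pearson, uncorrected: 180 × (5 × 90)²/(90 × 90 × 5 × 175) = 5.14 on 1 df, P = 0.023.
- Pearson with Yates correction: P = 0.070.

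The same table is significant by two of these and not by the other two. By two-sided Fisher, 4 v 0 gives 0.121 and 6 v 0 gives 0.029, so six against none is the smallest significant count. At 80 per group, 5 v 0 again gives 0.059. A four-group chi-square with all five cases in one group of 90 gives P = 0.0016, although it answers a different question.

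**Power of two-sided Fisher.** This sums the binomial probabilities of all tables with an excess in the supplemented group and P < 0.05. The true rates are assumptions, because the documents give none.

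| True rates | 80 per group | 90 per group | 180 v 180 |
|---|---|---|---|
| 3% v 0.5% | 2% | 4% | 26% |
| 5% v 0.5% | 15% | 21% | 69% |
| 10% v 0.5% | 72% | 80% | 99% |

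Uncorrected Pearson at 90 per group does better but is still weak: 19% for 3% v 0.5% and 47% for 5% v 0.5%. The 180 v 180 column uses enrolled numbers and assumes the same rate in both supplemented groups. With 160 evaluable per side, 5% v 0.5% gives 61%.

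**What an interval would show.**
- 5/90 v 0/90: the risk difference is 5.6 percentage points. The Wilson limits are 2.4% to 12.4% for 5/90 and 0 to 4.1% for 0/90. Newcombe lower limit: 5.56 − √((5.56 − 2.40)² + 4.09²) = 0.4. Upper limit: 5.56 + (12.35 − 5.56) = 12.4 (12.35 before rounding).
- Zero events, exact two-sided 95% upper limit, 1 − 0.025^(1/n): 4.0% for n = 90, 4.5% for n = 80 and 2.0% for n = 180.

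**Does pooling rescue the example?** No. With 5 v 0 at 180 per side, two-sided Fisher gives P = 0.061.

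**The case against.** The strongest reply has four parts.

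1. **Five v none need not be non-significant.** A reader might infer that the plan would necessarily report this table as showing no significant difference. The documents do not support that. Uncorrected Pearson and one-sided Fisher are both below 0.05, and the plan excludes neither. What stands is that Fisher is conventional at an expected count of 2.5 and that the outcome is not fixed in advance.
2. **The plan never equates non-significance with safety.** A reader might infer such a rule because P < 0.05 is the only criterion given, but that threshold is generic. Nor do the documents decide against pooling; they are silent on it.
3. **The tests on frequencies are not the only safety information.** Laboratory values can be compared as continuous variables under the same section, adverse events are recorded at each visit, and there are individual withdrawal criteria. These are genuine safeguards, but none gives a group-level estimate of excess harm with its uncertainty.
4. **Safety is an unpowered secondary objective, and the power figures depend on the rates chosen.** This is fair: an excess of 10% v 0.5% would be found in 72% to 80% of trials. Low power for rare harms is usual at this size, which is a reason to plan intervals rather than rely on tests.

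Intervals also depend on the method. For 5/90 v 0/90 the Newcombe interval excludes zero while two-sided Fisher does not reach 0.05, so the interval method must be named too.

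**Conclusion.** The point holds. For a stated objective with binary and probably uncommon outcomes, the plan's only between-group comparison of event frequencies is a test at P < 0.05, without an estimate or interval, and with test and sides left open. At 80 to 90 per group, two-sided Fisher would detect 5% v 0.5% in 15% to 21% of trials and 3% v 0.5% in 2% to 4%. A non-significant result could not support a safety conclusion, and even zero events in 90 leaves a risk of up to 4.0% open.

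The group sizes come from the plan; the event rates and counts are assumptions. The conclusion is limited to uncommon harms and to what the planned comparison can show. It does not say that the trial will declare supplementation safe, or that a 5 v 0 result must be called non-significant. This is a worthwhile improvement at low cost; it does not undermine the design.

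**What to change.** Add to the Statistical analysis section, for each safety outcome:
- the number and percentage of women with the event in each group, with an exact 95% confidence interval;
- the risk difference with a 95% confidence interval by a named method, for example Newcombe, for A v B and for C v D;
- as a supplement, a risk difference for A+C v B+D stratified by baseline vitamin D band, shown beside the two separate comparisons. The supplemented groups differ in dose and baseline band, so an excess confined to one of them would be diluted by pooling;
- a statement that P < 0.05 is not the safety criterion and that the conclusion is worded from the upper confidence limit, in the form that an excess above x percentage points is excluded. If P values are still shown, name the test and its sides in advance.

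The cost is SAP wording and slightly more analysis work, with no new patients, visits or data. The downside is that the safety conclusion will read less favourably than a bare statement of no significant difference.
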